- (10) Have any pending legal action that could prohibit continued participation.
- (11) Be expecting to leave the clinic=s geographic area prior to study completion.

PROCEDURES:

Patient Assignment and Length of Study: Eligible patients will be given an explanation of the study. Study participation will be 9 to 12 weeks for patients who successfully achieve detoxification and up to 12 months for patients requiring longer buprenorphine treatment.

This will be an open-label study with no random assignment or stratification. Each principal investigator (PI) may recruit up to 5-10 site physicians working in a variety of care delivery settings. Physician eligibility will be determined by the PIs and the sponsor (National Institute on Drug Abuse). Each site physician may admit up to 10-20 patients per site (90-110 patients per state). All patients will sign an informed consent approved by national and local Institutional Review Boards. Patients under 18 years of age must also obtain concurrent consent from a parent or guardian, as applicable. Prior to starting the study and after signing the informed consent, patients will receive the following:

A general medical and psychiatric evaluation, including a history of drug use and assessment of HIV risk, any medical or psychiatric illness requiring ongoing treatment, and any concomitant medications received either over the counter or under the prescription of a physician. Off-site HIV testing and HIV counseling will be encouraged.

A physical examination (to be repeated at the end of the study to the extent possible) to include vital signs, ECG for all patients over 40 and for patients under 40 with a history of cardiovascular disease, routine laboratory chemistry panel, urinalysis, and urine screen for drugs of abuse. Urinalyses will be performed weekly throughout the first 9 weeks of the study and periodically thereafter (for an anticipated maximum of 21 urine tests per 12 month treatment*) to test for drugs of

abuse. Females will also undergo pregnancy testing at baseline and monthly during their study participation.

Treatment Schedule: The following treatment schedule will apply according to the specific treatment setting assignment:

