Detoxification vs Maintenance: The decision to detoxify will be based on patient performance. As a minimum criterion for buprenorphine tapering, at least half of the urine samples obtained between weeks 3 and 6 must have been negative for opiates including the last sample obtained in week 6. If it is decided that detoxification should be attempted, the buprenorphine dose will be tapered over the next 3 weeks until, by week 9, Azero@ mg dose is achieved. The rate of taper will be individually determined. If detoxification appears impossible due to inability to achieve minimum criteria,

buprenorphine treatment will be continued for up to 52 total weeks. During this extended treatment period other treatment options will be explored or subsequent detoxification may be attempted.

Missed visits: Patients should be encouraged to keep their scheduled appointments. After two missed visits, patients should be considered for reinduction and dose scale up. Alternatively, patients may be re-evaluated for other types of therapy if compliance is poor.

Urine Screening for Drugs of Abuse: Urine samples will be obtained weekly for the first 9 weeks of treatment and assayed for the presence of opiates, benzoylecgonine, benzodiazepines, and amphetamines. Thereafter, an additional 12 urines* may be obtained if the patient stays in for the full year of treatment. Clinical decisions on extending the length of prescriptions for buprenorphine can be made, in part, on the urine results.

Psychosocial Treatment: In addition to the site physician=s visits, patients can receive psychosocial treatment from any of the following sources: an on-site medical assistant (trained to administer relapse prevention counseling), a drug counselor (on-site or off-site), or Narcotics Anonymous. For patients who will undergo detoxification, the psychosocial treatment will be extended to week nine and, thereafter, patients will be encouraged to enroll in aftercare self-help groups. Patients who require further treatment with buprenorphine will continue to participate in relapse-prevention programs at reduced frequency of visits. Patients receiving long-term buprenorphine/naloxone

treatment may receive up to 26 counseling sessions in the first year. In addition to the psychosocial treatment provided as part of this protocol, patients will be encouraged to attend other self-help support groups in the community (e.g., AA, NA).

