Post-Treatment Follow-Up: Patients will be contacted for a 30-day follow-up assessment of their post-treatment status. This will consist of self-report of whether the patient is currently using opiates

or other drugs illicitly and/or currently receiving substance abuse treatment (drug or alcohol). The patient will also be asked if they would take the study medication again if it were generally available for opiate dependence treatment. If the patient is deceased, the date and cause of death will be obtained and site staff will verify the information. This information will be captured on Form 12.

Pregnancy: Women of childbearing potential must have pregnancy tests performed monthly using an FDA approved device or method. Women becoming pregnant during the study will be referred to a methodone program.

Study Termination: Patients may be terminated from the study if the site physician determines that it is in the patient=s best interest (ex. safety concerns, etc.). A patient may also be removed for continued failure to keep appointments and for diverting or failure to handle medications

^{*}Additional tests may be performed if a therapeutic need arises.

responsibly. Women who become pregnant during the course of the study will be referred for methadone treatment. Patients who drop out or are terminated from the study will not be readmitted.

MEDICATION

Medication will be supplied free of charge from Reckitt and Colman through NIDA. Medication will be tamper-proof and labeled with the following warning:

ACaution: New Drug - Limited by Federal (or United States) Law to Investigational Use. @

The 4:1 combination tablet will be supplied in the 2mg/.5mg and 8mg/2mg buprenorphine/naloxone strengths. Medication will be supplied in blister packs as a one-week supply, and labeled as follows:

ABuprenorphine/naloxone combination tablets (2mg/.5mg and 8mg/2mg).

In case of emergency, please call:

(telephone number to be determined)@

Medication will be stored in a secure, limited-access location under the conditions specified by the label.

Medication Dispensing: The site physician will prescribe buprenorphine/naloxone for pick up at a specified local pharmacy. A two to four-week supply of medication will be the maximum dispensed

or prescribed at any time during the course of the study. Take-home medication will be provided according to the following schedule:

Week 1: Enough medication will be dispensed to last between visits by the site physician.

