The Clinical Global Impression Scale - Self is a patient-rated instrument of severity and global impression of change from the patient=s own perspective. The clinician will record the patient=s impression of their improvement on a 5-point scale from Amuch worse@ to Amuch improved.@ The severity item will be rated prior to enrollment and the global impression of change will be rated at each office visit throughout the study, including the follow-up visits. It should take less than 5 minutes to complete.

Physician=s Survey - Form 14

The Physician=s Survey is a questionnaire that each site physician will be asked to complete at the end of the study. It will record such information as usual prescribing patterns, adjustments required for

integration into their treatment setting, and ease and effectiveness of administration to a younger population.

Patient=s Survey - Form 15

The Patient=s Survey is a questionnaire that each patient will be asked to complete at the end of the study. It will record such information as the patient=s acceptability of office-based treatment, whether they felt that the office-based paradigm made it easier to be compliant, what their preferences would be and what adjustments, if any, that they found necessary to make.

Efficacy Evaluations

The outcome measures will include opiate use as determined by the urine drug screens, the clinical ratings from the opiate symptom checklist, the clinical global impression scales, and patient retention in the study. The primary focus will be on patient retention in the study and opiate use as determined by the urine drug screens.

Additional secondary outcome measures will include scores on the ASI, RAB, and opiate symptom checklist.

Safety Evaluations

Safety assessments will include a physical examination during the screening phase and upon termination from the study, laboratory tests taken during the screening phase and upon termination from the study, vital signs and urine drug screens obtained weekly, weekly evaluations by the site physician, and opportunities to report adverse events each week. In addition, monthly pregnancy tests will be performed on women of child-bearing potential.

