study drug dose, temporary cessation of study drug, or early termination of the trial. Any patient who receives at least one dose of study medication will be included in the evaluation for safety. Patients who do not receive at least one dose of study medication will be listed separately.

Compliance

Compliance to dosing will be measured via pill counts at each visit and by random medication callbacks. One callback will occur during the first 9 weeks of the study; and up to two more will occur during the remainder of the study.

Data Analysis

Power and Sample Size Considerations

Retention rate is one of the primary outcome measures and is a proportion. Many of the descriptions of the patients= use as determined by opiate positive urines may also be a proportion (e.g., percentage of subjects who have 6 consecutive clean urines). The maximum variability for a proportion occurs when the proportion equals one-half, thus any sample size estimate obtained for this proportion would be conservative in that it will require more subjects than actually needed. To compute a 95% confidence interval for the observed proportion, with precision of $\pm 5\%$, a sample size of approximately 400 is needed when the expected proportion is 0.5.

Since the dropout rate is expected to be between 70 and 80%, the total number of patients that need to be enrolled is between 500 and 575. This number has been rounded to 600 to permit each of the primary VA Medical Centers (across 6 states) to enroll about 100 subjects. Each site physician will be allowed to enroll between 10 and 20 subjects so that they gain sufficient experience to permit results to be generalized.

Demography and Baseline Outcome Analyses

The number of patients enrolled in the study will be summarized overall, by site and by treatment setting. For patients who are screened but not enrolled, a distribution of the reasons for discontinuation will be provided.

Demographic, as well as other pretreatment characteristics and baseline parameters, will be summarized overall, by site and by treatment setting.

Efficacy Analyses

Although the study design does not permit an unconfounded assessment of treatment efficacy, treatment improvement, or lack thereof, will be documented.

Patient retention rates will be the primary outcome measure and will be summarized using descriptive statistics, overall, by site and by treatment setting. The NIDA-VACSP Multicenter Buprenorphine

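### After week 9 the protocol fixes no timing for urine tests and does not separate need-driven samples from planned ones, so the later opiate results of maintained patients may be biased

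*Protocol*

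**What the plan says.** **Role of the urine results.** Protocol, Efficacy Evaluations: "The primary focus will be on patient retention in the study and opiate use as determined by the urine drug screens". Efficacy Analyses puts emphasis on the urine results and plans descriptive summaries overall, by site and by treatment setting, at end of treatment and separately at follow-up.

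**Weeks 1-9.** Urine Screening for Drugs of Abuse: "Urine samples will be obtained weekly for the first 9 weeks of treatment".

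**After week 9.** The same section continues: "Thereafter, an additional 12 urines* may be obtained if the patient stays in for the full year of treatment". The screening paragraph under Procedures has urines taken "periodically thereafter (for an anticipated maximum of 21 urine tests per 12 month treatment". The asterisk on both statements leads to a footnote: "Additional tests may be performed if a therapeutic need arises".

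**Clinical use of the results.** Urine Screening for Drugs of Abuse adds: "Clinical decisions on extending the length of prescriptions for buprenorphine can be made, in part, on the urine results". Under Medication Dispensing, supply is one week at a time to week 12. After that it is at the physician's discretion, up to two weeks in weeks 13-26 and up to four weeks in weeks 27-52.

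**A conflicting statement.** Safety Evaluations lists "vital signs and urine drug screens obtained weekly" among its assessments and gives no end week.

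**The concern.** For a maintained patient, 43 of 52 weeks have no stated urine schedule. Two features let the chance of being tested depend on the outcome being measured.

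- Tests on therapeutic need are open-ended, and a clinician is more likely to see a need when use is suspected. The protocol does not ask for these samples to be identified or kept out of the efficacy results.
- Urine results may feed into prescription length. The Treatment Schedule sets weekly visits for only three to six weeks after week 6, so from week 13 the supply length largely governs how often a patient attends. A patient with positive urines may be kept on short supply and seen more often. A patient with negative urines may move to a four-week supply.

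At stake are the opiate results for weeks 10-52, and the end-of-treatment result of any patient whose last urine falls in that period. Testing habits that differ between sites or settings could pass for differences in opiate use. This concerns data collection. An analysis plan can set aside need-driven samples only if they can be identified, and it cannot supply a schedule that was never set.

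**Working it through.** **1. The plan's own count.** Nine weekly urines plus 12 later ones: 9 + 12 = 21. This reproduces the stated maximum.

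**2. Coverage after week 9.** Weeks 10-52 are 52 - 9 = 43 weeks. Evenly spread, 12 urines fall every 43/12 = 3.6 weeks and cover 12/43 = 28% of the weeks. The protocol does not say that they are evenly spread.

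**3. Effect of spacing on the example endpoint.** Power and Sample Size Considerations gives as an example the "percentage of subjects who have 6 consecutive clean urines". Six weekly samples represent six weeks. Six evenly spaced later samples represent 6 x 43/12 = 21.5 weeks. Without a schedule the endpoint has no fixed meaning after week 9.

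**4. Conflict with Safety Evaluations.** Weekly screens through 52 weeks would make 52 tests, which is 52 - 21 = 31 more than the stated maximum. Both statements cannot describe the same patient.

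**5. Illustrative bias.** The inputs are assumptions, since the documents give none: true positivity p; odds ratio OR of a positive when the test is taken on suspicion; k such tests pooled with 12 taken at neutral times.

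- Positivity on suspicion: q = OR x p / (1 - p + OR x p)
- Pooled positivity: (12p + kq) / (12 + k)
- Example, p = 0.40, OR = 3, k = 6: q = 1.2/(0.6 + 1.2) = 0.667, and pooled = (4.8 + 4.0)/18 = 0.489

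| p | OR | q | pooled, k = 3 | pooled, k = 6 |
|---|---|---|---|---|
| 0.20 | 2 | 0.333 | 0.227 | 0.244 |
| 0.20 | 3 | 0.429 | 0.246 | 0.276 |
| 0.40 | 2 | 0.571 | 0.434 | 0.457 |
| 0.40 | 3 | 0.667 | 0.453 | 0.489 |
| 0.50 | 2 | 0.667 | 0.533 | 0.556 |
| 0.50 | 3 | 0.750 | 0.550 | 0.583 |

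The excess runs from 2.7 to 8.9 points. With OR = 1 or k = 0 it is zero.

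**6. Visits available for a schedule.** Assume that each resupply involves a visit. At the longest permitted supplies, weeks 10-12 give 3 visits, weeks 13-26 give 14/2 = 7, and weeks 27-52 give 26/4 = 6.5, about 16.5 in all. Twelve urines fit. Twelve equal blocks of 3.6 weeks do not, because under a four-week supply such a block may contain no visit. Six blocks over weeks 10-26 (17/6 = 2.8 weeks) and six over weeks 27-52 (26/6 = 4.3 weeks) do fit. In whole weeks, 17 = 5 x 3 + 1 x 2 and 26 = 4 x 4 + 2 x 5, so no block is shorter than the supply limit for its period.

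**The case against.** A reader might infer that the physician picks when the 12 urines are taken, and takes them on suspicion. The text says neither. It names nobody, and the permissive wording can be read as meaning only that the 12 depend on the patient staying for the year. Only the footnoted extra tests are tied to need. This stands, and it limits the point to a risk that the protocol leaves open.

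A reader might also infer a very large error. If all 12 urines were suspicion-driven, the formula above would give an excess of 13 to 27 points. The documents do not support that premise. The visit count also limits it: with about 16.5 visits and use at 40% of them, testing every use visit gives at most 6.6/12 = 55% positive. More frequent visits or uncapped extra tests would loosen that bound.

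Nor can it be said that the reason for testing goes unrecorded and that no analysis could repair the result. The urine form and any SAP are not at hand, and a SAP could exclude unscheduled samples if they are identifiable. What remains is that the protocol does not require them to be identifiable.

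Three further limits stand. The ±5% precision applies to patient-level proportions and is no yardstick for a sample-level positivity rate. No positivity rate for weeks 10-52 is named as an endpoint, and Efficacy Analyses calls retention the primary outcome measure. That section also concedes that the design gives no unconfounded assessment of efficacy. But that caveat concerns attributing change to treatment. It does not cover measuring opiate use with error, and the end-of-treatment urine summary still depends on when the last sample was taken.

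The weekly screens in Safety Evaluations do not supply the missing schedule, since they contradict the 21-test maximum.

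**Conclusion.** The concern holds as a risk of bias built into data collection. After week 9 the protocol sets no urine timing, permits uncapped need-driven tests, does not require them to be separated, and lets urine results influence how often a patient attends. The affected results are those of maintained patients in weeks 10-52 and at end of treatment, including the comparisons by site and setting. The weekly tests to week 9 are not affected.

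The size cannot be derived from the documents. An excess of about 3 to 9 points follows if 3 to 6 suspicion-driven tests are pooled with 12 neutral ones, with true positivity of 20% to 50% and odds of a positive two to three times higher on suspicion. It is zero if timing is unrelated to use, but nothing in the protocol secures that. The protocol should be changed on this point, because the remedy is cheap and has to be in place before the samples are taken.

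**What to change.** 1. Pre-assign the same 12 urines for each maintained patient. Use six blocks of about 2.8 weeks over weeks 10-26 and six of about 4.3 weeks over weeks 27-52. In each block the coordinating center draws one visit in advance. The blocks fit the existing supply limits, provided that each resupply involves a visit.
2. Mark every sample on the form as scheduled or for cause.
3. Base urine efficacy summaries on scheduled samples, and report for-cause samples separately. For-cause testing stays at the physician's discretion.
4. Reconcile the weekly urine screens in Safety Evaluations with the maximum of 21 under Procedures and the 9 plus 12 under Urine Screening for Drugs of Abuse.

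The planned total stays at 21 and the sample size does not change. The cost is a visit list per patient, one form field and minor scheduling work. The draw removes bias from the timing of tests only; it does not address patients who leave the study.

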Patients will be interviewed and monitored weekly for adverse experiences throughout the treatment period under the direct close supervision of the investigator or designated staff. All adverse experiences, either observed by the site physician or one of his/her professional colleagues, or reported by the patient spontaneously or in response to a direct question will be noted in the adverse events section of the patients Case Report Form.

The site physician or designated staff will evaluate the intensity, seriousness, and causal relationship to the study medication of all adverse experiences whether or not thought to be drug related. Any adverse experience will be recorded and listed on the CRF. The IRB and the sponsor, NIDA, will be informed by telephone within 24 hours by the investigating institute of any serious adverse experiences. A written report to NIDA will follow within three days. All serious adverse events will be reported whether or not considered drug-related.

Definitions of serious, unexpected or life-threatening experiences are summarized below.

Serious Adverse Experiences: Any adverse experience that is fatal or life-threatening, results in persistent or significant disability or incapacity, requires inpatient hospitalization or prolongation of hospitalization, requires intervention to prevent permanent impairment or damage, or is a congenital anomaly/birth defect.

Unexpected Adverse Experiences: Any experience that is not identified in nature or severity in the current literature (e.g., Investigator=s Brochure, Buprenex labeling).

Life-Threatening Experiences: Patient is, in the view of the site physician, at IMMEDIATE risk of death from the reaction as it actually occurred. This definition does not include reactions that might be fatal if they were to occur in a more severe form.

In addition, any overdose should be reported to NIDA within 24 hours.

A complete list of definitions for the terms used to describe clinical and laboratory adverse experiences is given in Appendix I. The regulatory reporting time frames are also given in this appendix.

In the event of an adverse event felt to reflect drug-related toxicity, appropriate evaluation and management will be undertaken and may include, in addition to medical management, a reduction in

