Study #999A, a 16-week efficacy and safety study using a traditional clinical trial setting, has shown a retention rate of 51%. About 82% of those completers, chose to enter the #999 Extension Study which provided for an additional 36 weeks of maintenance. Of the patients entering the extension study, 57% completed a total of 52 weeks (this would be a 24% retention rate for all patients enrolled). In the NIDA-VACSP Multicenter Buprenorphine Studies #1008A and B, a retention rate of about 30% was seen for 52 weeks for all patients enrolled.

The proposed length of patient accrual for this study is estimated to be 20 weeks. This is based upon the assumption that 5 patients will be able to be recruited in each state per week. A patient=s participation in the study can last up to 1 year with follow-up being conducted thirty days after their completion/termination in the study. Accounting for the needs for data edits and clarifications, the total length of the study at each site is estimated to be 2 years.

Emphasis also will be placed on the urine toxicology screen results, the self-reports of drug use and the clinician rating of improvement obtained at the end of treatment. Other self-reports and ratings will be considered secondary. The results (actual values and change from baseline) will be summarized using descriptive statistics overall, by site and by treatment setting. These summaries will be performed for the end of treatment, and for the follow-up separately.

The effects of the medication itself, as well as, the effects of withdrawal from opiates will be measured. The results will be summarized using descriptive statistics overall, by site and by treatment setting.

The Office Visit Checklist (Form 09) contains information on the treatment prescribed (induction, maintenance, dose taper) and on the actual prescription (amount, frequency, duration). The information from this checklist will be summarized using descriptive statistics. At a minimum, the summaries will be prepared overall, by site and by treatment setting. Further summaries by induction, maintenance and/or dose-tapering may be performed.

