Appendix I

ADVERSE EVENTS

The sponsor should be notified (e.g., by telephone, facsimile transmission, or in writing) as soon as possible but no later than 24 hours after first knowledge by the investigator that a case qualifies, followed by as complete a report as possible within 5 additional calendar days. This report should include an assessment of the importance and implication of the findings, including relevant previous experience with the same or similar medicinal products.

All Other Serious, Unexpected ADRs

Serious, unexpected reactions (ADRs) that are not fatal or life-threatening must be communicated to the sponsor as soon as possible but no later than 5 calendar days after first knowledge by the investigator that the case meets the minimum criteria for expedited reporting.

Minimum Criteria for Reporting

Information for final description and evaluation of a case report may not be available within the required time frames for reporting outlined above. Nevertheless, for regulatory purposes, initial reports should be submitted within the prescribed time as long as the following minimum criteria are met: an identifiable patient; a suspect medicinal product; an identifiable reporting source; and an event or outcome that can be identified as serious and unexpected, and for which, in clinical investigation cases, there is a reasonable suspected causal relationship. Follow-up information should be actively sought and submitted as it becomes available.

How to Report

The MedWatch form has been a widely accepted standard for expedited adverse event reporting. All reports must be sent to the sponsor.

Post-Study Events

Serious adverse events that occurred after the patient had completed the clinical study (i.e. during follow-up) should be reported by an investigator to the sponsor. Such cases should be regarded for expedited reporting purposes as though they were study reports. Therefore, a causality assessment and determination of expectedness are needed for a decision on whether or not expedited reporting is required.

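### The 30-day contact has no question on non-fatal serious events, although Appendix I expects serious events in follow-up to be reported, so their ascertainment after treatment is passive and likely incomplete

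*Protocol*

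**What the plan says.** **What is asked at 30 days.** Under Post-Treatment Follow-Up, the content of the contact is set out as a list. It opens with opiate use: "This will consist of self-report of whether the patient is currently using opiates". The same sentence then widens the self-report to further drugs and to treatment: "or other drugs illicitly and/or currently receiving substance abuse treatment (drug or alcohol"). To this are added an acceptability item, "The patient will also be asked if they would take the study medication again", and death: "If the patient is deceased, the date and cause of death will be obtained and site staff will verify the information". All of it goes on Form 12. The Efficacy Analyses section places the contact in time, "with follow-up being conducted thirty days after their completion/termination in the study".

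**When adverse events are actively sought.** Under Safety Evaluations: "Patients will be interviewed and monitored weekly for adverse experiences throughout the treatment period".

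**What is to be reported.** Safety Evaluations asks for all serious events to be reported whatever their suspected cause, and adds: "In addition, any overdose should be reported to NIDA within 24 hours". Appendix I, Post-Study Events, states: "Serious adverse events that occurred after the patient had completed the clinical study (i.e. during follow-up) should be reported by an investigator". It goes on to say that such cases need a causality assessment and a decision on expectedness. The Appendix I definition of serious includes inpatient hospitalisation.

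**The concern.** The protocol creates a reporting duty for the follow-up period and schedules a contact at its end, but the contact as described does not ask the question that would serve the duty. Death is the only serious outcome on its list.

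This matters because the introduction gives safety in office-based care as the reason for the study and says the data will be used to expand labeling. The 30 days after treatment follow a taper, a dropout or a removal, and the patient is no longer seen weekly. Medication Dispensing allows up to a four-week supply in weeks 27-52, so a patient who leaves then may still hold study tablets. An event in this window could therefore be related to the study drug as well as to relapse.

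If non-fatal events reach the site only by chance, a low count after treatment cannot be told apart from a low rate of asking. An analysis plan cannot repair this, because it concerns what patients are asked.

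**Working it through.** The protocol states no figure on this point, so there is nothing to reproduce. The check sets the duty beside each source of information after treatment.

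**Step 1. Seriousness criteria against the 30-day list.**

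| Outcome (Appendix I definition; overdose from Safety Evaluations) | Item at the 30-day contact? |
|---|---|
| Death | Yes, date and cause, verified |
| Life-threatening event, non-fatal | No |
| Inpatient hospitalisation or its prolongation | No |
| Persistent or significant disability | No |
| Congenital anomaly | No |
| Other important medical event | No |
| Non-fatal overdose | No |

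The two drug-use items concern current use and current substance abuse treatment. Neither asks about an event since the last dose.

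**Step 2. Other sources that might cover the window.**

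- *Weekly adverse-event interviews* (Safety Evaluations): confined to the treatment period.
- *Physical examination and laboratory tests at termination* (Safety Evaluations): done at exit, before the 30 days begin.
- *Opiate Symptom Checklist and the two Clinical Global Impression scales, Form 09* (Measures): also rated at follow-up visits, but they record withdrawal symptoms and global change.
- *Survey of resource utilisation in follow-up* (Efficacy Analyses): could pick up a hospitalisation, but no items are given, the results are exploratory and narrative, and no route to event reporting is described.
- *Spontaneous reports to the site*: possible at any time, and covered by Appendix I once known. This is passive ascertainment.

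No source is described as an active enquiry about non-fatal serious events after treatment.

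**Step 3. Size of the window.** Inputs: 600 patients (Study Design) and 30 days (Efficacy Analyses).

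600 x 30 / 365.25 = 18,000 / 365.25 = 49.3 person-years.

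This is an upper bound. It assumes that the full 600 are enrolled and that each contributes all 30 days.

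**The case against.** **The 30-day call is not the only information after treatment.** Form 09 ratings are made at follow-up visits, two of the three instruments are clinician-rated, and patients are surveyed on resource use. This stands, and it rules out describing Form 12 as the sole planned contact. It does not close the gap, because the ratings cover withdrawal and global change and the survey's content is unstated. The narrative summary of the survey is not itself the weakness: a hospitalisation learned of in that way should still be reported under Appendix I. The weakness is that nothing says hospitalisation is asked about there or that an answer is passed on.

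**A duty exists, and passive reporting can meet it.** Appendix I places the duty on the investigator and does not promise active questioning. The overdose sentence has no stated end date, and patients carry a card with an emergency number. This also stands, so the documents do not support saying that these events *will* be missed. They support saying that the events are not asked about and may be missed. Appendix I also says that follow-up events should be reported, not that they must, and the overdose sentence does not say that it extends past treatment.

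**The forms are not shown.** Form 12 may hold more items than the protocol describes. That is possible, but the protocol describes the contact as consisting of the listed items, and sites will work from that description. If Form 12 already asks about serious events, the protocol text should say so.

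**Conclusion.** The point holds as a gap between duty and data collection. Followed as written, the plan verifies deaths at 30 days but has no stated enquiry about non-fatal overdose, hospitalisation or other serious events. Ascertainment in that window is passive and likely incomplete. The window is at most about 49 person-years. The conclusion rests on reading the Post-Treatment Follow-Up list as complete, which is how it is worded. No sample-size or precision figure changes.

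A reader might infer more, and the documents do not support it:

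- *That Appendix I leaves out dropouts and terminated patients because it speaks of those who completed.* The same sentence equates that time with follow-up, and Efficacy Analyses applies follow-up to completion and termination alike. Read together, these patients are covered.
- *That 420-480 patients would be non-completers (0.70 x 600 to 0.80 x 600).* This takes the stated 70-80% dropout at face value. The enrolment of 500 to 575 derived from it matches 70-80% *retained* (400 / 0.80 = 500; 400 / 0.70 = 571). The non-completer share is therefore unsettled in the protocol.
- *That some particular number of events would be lost.* An assumed 2-10 per 100 person-years would give about 1 to 5 events (49.3 x 0.02 to 49.3 x 0.10). The protocol gives no such rate, and the count also supposes that nothing is reported spontaneously or through the survey.
- *That the lack of a separate post-treatment safety table is a fault.* That may be left to the analysis plan.

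**What to change.** In Post-Treatment Follow-Up and on Form 12, add a question on any overdose, any hospitalisation and any other serious event since the last dose, with dates. Put it to every patient, whether they completed, dropped out or were terminated. State that a positive answer enters the reporting and causality process described in Appendix I under Post-Study Events.

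The contact and the form are already planned, so the cost is a few extra items and some additional reports to process. Treatment, visit schedule and sample size are unaffected.
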